The potential risks in this study are minimal and involve risks of 1) confidentiality; 2) the fMRI procedure; 3) insertion of intravenous catheters and needles (for IV alcohol administration and blood draws); 4) administration of alcohol; and 5) pregnancy testing.

1. Confidentiality: Laboratory personnel strictly maintain confidentiality, and records are kept in a secure location. However, there is a risk that a volunteer's Protected Health Information (PHI) may be seen by others. PHI is considered individually identifiable health information transmitted or maintained in any form (i.e., electronic means, on paper, or through oral communication) that relates to the past, present, or future physical or mental health conditions of an individual that may be used or disclosed. The following PHI will be collected as part of this project: name, address, telephone number, Social Security number, dates (birth, admission, discharge), medical record numbers, mental and physical health history, drug use history, results from mental and physical health screening, and data from experimental measures. All data will be coded by participant number only and any personal identifiers linking participants to their reports on questionnaires will be detached and destroyed as soon as participation is completed or disqualification occurs.

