2. fMRI procedure: fMRI is a non-invasive procedure that is widely used and safe. Potential risks such as static magnetic field, radio-frequency field, magnetic field gradients, and acoustic noise are rarely dangerous or life-threatening. The risks of the study are extremely small when exclusion criteria are observed and are outweighed by the large benefits of these studies to clinical and neuroscience research. Subjects will be asked questions about claustrophobia and the presence of metal in their body to make sure that the MRI scan is safe. If they have implanted metal of any kind, they will not be scanned. For their safety, they will be asked to remove any metal in their clothing before the scan (for example, belts and rings). Subjects will be given noise dampening head phones to reduce the discomfort due to the noise of the machines. Subjects are asked to report any discomfort immediately. They may discontinue the scan at any time if they are too anxious to continue, by communicating with the scanning operator that they would like to end the session. Additional minor or rare risks include: i) discomfort from lying still for 1 hour; ii) fast imaging sequences may potentially induce peripheral nerve stimulation (PNS) that may cause mild discomfort but is not harmful to participants; iii) anxiety or panic attack caused by close confinement in the scanner; iv) the MRI may reveal a minor or significant lesion in the brain (e.g., tumor) previously unknown to the subject. The CRC nurse and PI and also the Study Physician will be available and/or present during the fMRI scans in order to evaluate the emergence of any anxiety/panic attack, elevated levels of anxiety, or emotional discomfort during the procedure.

3. Insertion of needles/catheters: Some risks are associated with the insertion of intravenous catheters. These include bruising and pain at the site of the needle insertion, and a small risk of infection. A trained CRU nurse will perform blood draws and catheter insertion to minimize pain and standard sterilization techniques and other routine precautions will be utilized in order to minimize the risk of needle-site infections.

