Subjects will attend an orientation session during which they will sign the consent form and be instructed on the procedures of the study. All subjects will be monitored for recent alcohol and drug use prior to each session. Those with positive tests will be rescheduled or dropped from the study. All fMRI sessions are conducted in a hospital setting. During the sessions, emergency medical assistance will be available by paging the Study Physician, the psychiatrist resident on call, or the general emergency number for the hospital. Alternately, the subject may be transported to the emergency room. All adverse events (AEs) and unanticipated problems occurring during the course of the study will be reported to the IRB by the PI. All AEs will be followed until resolved satisfactorily. If deemed necessary by a physician, a subject may be withdrawn from the study. AEs will be evaluated for serious adverse event (SAE) criteria (defined by the FDA). If an SAE should occur, it will be reported to the IRB, NIAAA, and the FDA. The initial report will be followed by a complete SAE report, sent to all three institutions. If a subject from the study or the investigator discontinues a subject's participation due to an SAE, the patient will receive follow-up medical care as necessary. Follow-up care will continue until the subject no longer requires hospitalization, the condition is stabilized with no future change expected, or the problem is determined to be unrelated to the alcohol administered in the study. The outcome of the SAEs will be reported to NIAAA. The annual progress report submitted to NIAAA will contain a summary of any SAEs occurring in the previous year.

[Back to Top](#)

Future Use and Sharing of Material (e.g., Data/Specimens/Information)

If the material collected for this study will be used by members of the research team or shared with other researchers for future studies, please address the following:

- list the biological specimens and/or information that will be kept
- briefly describe the types, categories and/or purposes of the future research
- describe any risks of the additional use
- describe privacy/confidentiality protections that will be put into place
- describe the period of time specimens/information may be used
- describe procedures for sharing specimens/information with secondary researchers
- describe the process for, and limitations to, withdrawal of specimens/data

N/A

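### Care after an SAE discontinuation may stop once alcohol is ruled out as the cause, even if another study procedure caused the injury (narrow wording point)

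*Combined protocol and SAP*

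**What the plan says.** The rule is in the Safety Monitoring Plan, under Data and Safety Monitoring. It concerns a subject whose participation is discontinued "due to an SAE, the patient will receive follow-up medical care as necessary". The plan then sets how long that care lasts. It gives two end points first: "Follow-up care will continue until the subject no longer requires hospitalization, the condition is stabilized with no future change expected". It then adds a third: "or the problem is determined to be unrelated to the alcohol administered in the study". The three end points are alternatives, so any one is enough.

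The same section has two wider provisions. One applies to every adverse event: "All AEs will be followed until resolved satisfactorily". The other applies during sessions: "emergency medical assistance will be available by paging the Study Physician". Neither depends on the cause of the event.

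Potential Risks & Benefits lists the physical risks of taking part as separate items: "2) the fMRI procedure; 3) insertion of intravenous catheters and needles (for IV alcohol administration and blood draws); 4) administration of alcohol". On the scan it says: "The risks of the study are extremely small when exclusion criteria are observed". On catheters and needles it says: "These include bruising and pain at the site of the needle insertion, and a small risk of infection".

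Study Design pairs an alcohol session with a saline session in each phase and counterbalances dose order, so some subjects receive saline first.

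**The concern.** The commitment to care is wider at entry than at exit. It is triggered by an SAE, which the plan defines by seriousness and not by cause. The first two end points also ignore cause. The third asks about cause but names only alcohol.

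Both kinds of session also involve a catheter, blood draws, an infusion and an MRI, all done for research. A serious injury from one of these would be caused by the study and yet be unrelated to alcohol. On the literal wording, the specific promise of care could then lapse while the subject was still in hospital and unstable.

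What is at stake is a written protection for volunteers. The trial's inference is not involved.

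**Working it through.** No arithmetic applies, and the plan gives no figure to reproduce. The check is to read the stopping rule against the procedures and risks described elsewhere.

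**Inputs**
- Trigger for care: discontinuation because of an SAE, whatever the cause (Safety Monitoring Plan).
- End points: (a) hospitalization no longer required; (b) condition stable; (c) problem judged unrelated to the alcohol given. They are joined by *or* (same place).
- Procedures other than alcohol: MRI, catheter, blood draws and saline infusion (Research Procedures, under Brain Imaging Sessions and Infusion Procedure).
- Order: alcohol and saline are counterbalanced (Study Design).

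**Step 1. When does the third end point decide the matter?** Take a subject discontinued because of an SAE.
1. Hospitalization no longer required: (a) already ends care. The third end point is not needed.
2. Still hospitalized but stable: (b) already ends care. Again the third is not needed.
3. Still hospitalized, unstable, problem related to alcohol: none of the three is met, so care continues.
4. Still hospitalized, unstable, problem unrelated to the study in any way: (c) is met. This is presumably what the clause is for.
5. Still hospitalized, unstable, problem caused by the MRI, catheter, blood draw or saline infusion and not by alcohol: (c) is also met, although the study caused the injury.

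Only case 5 gives the wrong result. It needs an SAE, discontinuation because of it, a continuing need for hospitalization, no stabilization, and a judgement that alcohol was not the cause, all together.

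**Step 2. Can case 5 arise?** Yes. The clearest instance is a subject whose first session is saline. No study alcohol has been given by then, so any injury at that session is necessarily unrelated to it. The risk section does not rule out serious harm from the other procedures: it describes the scan risks as rarely dangerous and names infection as a small risk of catheter insertion. Bruising and needle pain would not ordinarily be serious, so a serious infection is the realistic catheter example.

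**Step 3. Does any other provision rewrite the clause?** None does, but several narrow the gap.
- The duty to follow every adverse event until it resolves covers SAEs too and has no test of cause. It speaks of following the event and does not expressly promise medical care.
- Emergency assistance is not limited by cause but is described for the sessions. A catheter infection could appear later.
- In the list of protections under Records, Privacy, and Confidentiality, the MRI item (item 8) says side effects will be treated by available physicians and nurses. This is an express treatment commitment for a procedure other than alcohol, in the setting of the scan.
- Item 2 of that list provides medical consultation and 24-hour on-call support, tied neither to alcohol nor to session hours. It gives access to help and does not say how long care lasts.
- The alcohol item under Potential Risks & Benefits counts injection-site pain as a possible effect of alcohol. In an alcohol session, some infusion-site problems might therefore be judged alcohol-related, which would keep them outside the third end point.

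**Step 4. What would the replacement change?** If the test becomes unrelatedness to any study procedure, cases 1 to 4 come out as before. Case 5 no longer meets (c), and care continues.

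**The case against.** The strongest reply is that the plan should be read as a whole. An SAE is an adverse event, and every adverse event is followed to satisfactory resolution whatever its cause. On that reading the third end point can close the special care clause but not the general duty. Scan side effects are to be treated, on-call support is available around the clock, and *the alcohol* may simply be shorthand for the study intervention. The protocol does not draw a clean line between alcohol and catheter effects either, since it lists injection-site pain under alcohol. Finally, the consent pages are not in the public document, and injury terms there could settle the point.

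Much of this stands, and it is why the point is minor. It does not remove the point. The plan gives post-discontinuation medical care its own stopping rule, separate from the sentence on following events, and someone applying the section would use the specific rule for care. The scan and on-call provisions do not set how long care lasts. If shorthand was meant, even *the intervention* would not clearly cover an MRI or a blood draw, and the edit would only state the intent. The overlap between infusion-site effects and alcohol is no help in a first saline session. Nothing is inferred from the absence of the consent pages.

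A reader might go further and infer that the plan tells staff to withdraw care from injured subjects, or leaves them unprotected. The documents do not support that: no sentence directs withdrawal, and the provisions above remain in force. Nor is adverse event follow-up or SAE reporting limited to alcohol-related events; neither carries a relatedness condition.

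**Conclusion.** The point holds as a narrow wording defect. One of three alternative end points for care tests relatedness to alcohol only. Read literally, it gives the wrong result for a subject seriously injured by another study procedure who is still hospitalized and unstable. Other provisions cover that case in part but do not change the clause.

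The conclusion assumes that *or* and *the alcohol* are read literally, and that following an event is not the same as providing medical care. The plan defines neither of those last two terms. If the sponsor means them as one, or if the consent form covers injury more broadly, the practical gap shrinks further.

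No size of harm is claimed. The documents give no SAE rate and describe the risks as minimal. It would be tempting to count sessions or blood draws as a measure of the problem, but such counts show only how often the procedures take place. The primary outcome, the analysis and the sample size are unaffected. This is a cheap improvement to consider.

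**What to change.** In the Safety Monitoring Plan, change the closing words of the third end point so that the problem must be *unrelated to any study procedure (alcohol or saline infusion, catheterization, blood draw, MRI)*. Apply it in the same way to alcohol and saline sessions.

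The cost is one phrase in the protocol. No procedure, data item or analysis changes. The small downside is possibly longer care in a rare event.

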**Attachments**

Attach Type	File Name
Study Drug Form	Ethanol_Side Effects, Dosages, Treatment, Interactions, Warnings.pdf
Study Drug Form	Study.Drug.Form.pdf
Study Drug Form	Alcohol_monograph.pdf
Study Drug Form	CofA Lot# 01RM1504A Ethanol.pdf
Study Drug Form	Ethanol_Label_Primary.pdf

Statistical Analysis Plan. *Statistical Analysis of Brain Activation:* The measures of brain activation during response inhibition (BARI) are activation in frontal ROIs (e.g., DLPFC, IFC, ACC, pre-SMA, SMA, and pre-motor cortex), as measured by BOLD % signal change, examined during response inhibition [StopInh>Go]. We will first check that men and women are matched on demographics and drug and alcohol use, and confirm that the [StopInh>Go] contrast activated the inhibitory network circuitry.

Statistical Analysis of Brain Activation: We will perform regression analyses in SPM12 to assess the degree to which baseline hormone levels predict change in BARI following alcohol compared to saline [StopInh>Go, Saline>Alcohol]. We hypothesize that greater baseline E2 will predict less activation following alcohol compared to saline. We will conduct a between-subjects t test to compare men and women on the StopInh>Go, Saline>Alcohol contrast. We hypothesize that alcohol effects on BARI will be greater in women compared to men. Finally, we will calculate change scores (alcohol minus baseline) for hormone levels, and perform regression analyses to predict [StopInh>Go, Saline>Alcohol] from change in hormone levels. We hypothesize that greater alcohol-induced increase in E2 will predict greater decrease in activation following alcohol.

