The overall objective of the research is to identify hormonal determinants of alcohol effects on brain activation during response inhibition (BARI) in young adult female and male drinkers. BARI will be assessed using fMRI during performance of the stop signal task. This task reliably activates right-lateralized prefrontal regions implicated in inhibitory control. We will assess BARI during IV alcohol (60mg%) and saline infusion in women during the early follicular and mid-luteal phases and in men at matched intervals. Aim 1: To determine the influence of circulating sex hormones on BARI responses to alcohol. Based on the positive relation between estradiol and BARI in sober heavy drinking women, we hypothesize that baseline levels of estradiol will be positively related to BARI following alcohol. Aim 2: To determine the effects of menstrual cycle phase on BARI responses to alcohol. We hypothesize that women will be more sensitive to the impairing effects of alcohol on BARI in the early follicular phase, when hormone levels are low. Aim 3: To determine the degree to which alcohol effects on sex hormones influence alcohol effects on BARI. We hypothesize that less alcohol-induced increase in estradiol will predict greater alcohol-induced decrease in BARI. Aim 4: To determine sex differences in BARI responses to alcohol. Based on our previous findings that heavy drinking women show less BARI than men when sober, we hypothesize that women will display greater alcohol-induced decrease in BARI than men, and that the sex difference will be most pronounced for women in the early follicular phase.

Study Design

Describe and explain the study design (e.g., observational, secondary analysis, single/double blind, parallel, crossover, deception, etc.).

- *Clinical Research:* Indicate whether subjects will be randomized and whether subjects will receive any placebo.
- *Community-Based Participatory Research:* If you are conducting [community-based participatory research \(CBPR\)](#), describe strategies for involvement of community members in the design and implementation of the study, and dissemination of results from the study.
- *Qualitative research:* Indicate ranges where flexibility is needed, if a fixed interview transcript is not available, describe interview topics including the most sensitive potential questions.

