- *Research Repositories:* If the purpose of this submission is to establish a Research Repository (bank, registry) and the material you plan to collect is already available from a commercial supplier, clinical lab, or established IRB approved research repository, provide scientific justification for establishing an additional repository collecting duplicate material. Describe the repository design and operating procedures. For relevant information to include, see the [UK Research Biospecimen Bank Guidance](#) or the [UK Research Registry Guidance](#).

This study will use a within- and between-subjects, placebo-controlled, single-blind design in a sample of female (N=30) and male (N=30) young adult heavy drinkers. Subjects will attend four fMRI sessions (two in the early follicular phase and two in the mid-luteal

phase for women, and at matched intervals for men) in which they perform the stop signal task and a resting state undergoing either IV alcohol (60mg%) or saline infusion (placebo). Alcohol and saline sessions within each phase will be separated by 24-48 hours. Dose and phase order will be counter-balanced. Blood samples will be collected at baseline and during infusion to assess levels of estradiol, progesterone, and testosterone. The primary outcome measure will be brain activation during response inhibition.

Attachments

Subject Recruitment Methods & Advertising

Describe how the study team will identify and recruit subjects. Please consider the following items and provide additional information as needed so that the IRB can follow each step of the recruitment process.

- How will the study team identify potential participants?
- Who will first contact the potential subjects, and how?
- Will you use advertisements? If so, how will you distribute those?
- How and where will the research team meet with potential participants?
- If applicable, describe proposed outreach programs for recruiting women, minorities, or disparate populations.
- How will minimize undue influence in recruitment?
- Attach copies of all recruiting and advertising materials (emails, verbal scripts, flyers, posts, messages, etc.).

For additional information on recruiting and advertising:

- [IRB Application Instructions - Advertisements](#)
- [PI Guide to Identification and Recruitment of Human Subjects for Research](#)

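### The primary outcome is an open list of frontal regions tested in three analyses with no inference level, threshold or correction, and the SAP reverses the Aim 3 estradiol prediction

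*Combined protocol and SAP*

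**What the plan says.** **Outcome.** Study Design states: "The primary outcome measure will be brain activation during response inhibition". It names no region. The Statistical Analysis Plan (SAP) gives the measures as "activation in frontal ROIs (e.g., DLPFC, IFC, ACC, pre-SMA, SMA, and pre-motor cortex), as measured by BOLD % signal change", for the contrast of correct stop trials against correct go trials. The list opens with *e.g.*, so it is illustrative. No mask, coordinates or hemisphere is given. The Objectives remark that the task activates right-lateralised prefrontal areas describes the task and does not define a region.

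**Analyses.** The SAP applies the saline-versus-alcohol contrast in three places:
- a baseline regression: "We will perform regression analyses in SPM12 to assess the degree to which baseline hormone levels predict change in BARI";
- a t test of women against men;
- a regression on change in hormone levels.

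No section gives an alpha, sidedness, voxel or cluster threshold, whole-brain or small-volume choice, or correction. Three hormones are assayed, and the regressions are worded for hormone levels in general. The hormone hypotheses name estradiol only.

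**Sessions.** "Subjects will attend four fMRI sessions (two in the early follicular phase and two in the mid-luteal" phase, with men at matched intervals. Each person therefore yields two alcohol–saline contrasts. The SAP does not say how they enter the tests.

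**Direction of the estradiol predictions.**

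| | Objectives | SAP |
|---|---|---|
| Baseline E2 | Aim 1: "we hypothesize that baseline levels of estradiol will be positively related to BARI following alcohol" | "We hypothesize that greater baseline E2 will predict less activation following alcohol compared to saline" |
| Change in E2 | Aim 3: "We hypothesize that less alcohol-induced increase in estradiol will predict greater alcohol-induced decrease in BARI" | "We hypothesize that greater alcohol-induced increase in E2 will predict greater decrease in activation following alcohol" |

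**The concern.** A single declared primary outcome should lead to a result that can be called positive or negative by a rule fixed in advance. Here the analyst could choose the regions, the type of inference and the threshold after seeing the data, and one significant region could be reported as support for the primary hypothesis. The estradiol conflict adds to this. With one sign predicted in the Objectives and another in the SAP, a chance finding of either sign in the hormone-change regression could be presented as the expected one. The baseline regression is exposed in a weaker way.

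**Working it through.** The plan gives no alpha, power or effect size, so there is no figure of its own to reproduce.

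**1. Inputs.** From the documents: six named regions, three analyses, 30 women and 30 men. Assumed: inference on one extracted value per region and participant, two-sided 0.05 per test, normal data, and equal correlation between regions of 0.3 to 0.9.

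**2. Independent regions (upper reference).**
- Either sign, six tests: 1 − 0.95^6 = 0.265.
- One sign only, six tests: 1 − 0.975^6 = 0.141.

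**3. Correlated regions.** Null simulation with 20,000 runs per setting, giving the chance of at least one false-positive region in one analysis:

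| Correlation between regions | 0.3 | 0.5 | 0.7 | 0.9 |
|---|---|---|---|---|
| Either sign | 24–25% | 20–22% | 16–17% | 11% |
| Sex test, hypothesised sign only | 12–13% | 10% | 8–9% | 5.5–5.9% |
| Either sign, each test at 0.05/6 | 4.5–4.9% | 3.9–4.4% | 3.2–3.6% | about 2% |

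The either-sign row is much the same for a regression on 60 participants or on 30 women. The SAP does not say which it intends. It is the relevant row for the regressions while the predicted sign is unsettled. The sex hypothesis has the same direction in the Objectives and the SAP, so the second row applies to it.

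**4. Phases.** If the sex test were run separately in each phase (12 tests), the independent figure is 1 − 0.95^12 = 0.460. Simulation gives 24–42% at region correlations of 0.7 to 0.3, with between-phase correlation 0.2–0.8. Correcting for six tests only would leave 5.3–8.9%, so a six-region correction does not cover 12 tests.

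**5. Estradiol signs.** Let S and A be activation under saline and alcohol, and D = S − A the fall caused by alcohol.
- *Change in E2.* Aim 3 says a smaller rise goes with larger D, a negative association. The SAP says a larger rise goes with larger D, a positive one. Both concern the same two quantities, so this is a direct reversal.
- *Baseline E2.* Aim 1 says cov(E2, A) > 0. The SAP says cov(E2, D) > 0. Since A = S − D, cov(E2, A) = cov(E2, S) − cov(E2, D). Both can hold if cov(E2, S) exceeds cov(E2, D), and the Objectives do report a positive relation between estradiol and BARI when sober. The two statements are in tension but are not logical opposites. Aim 2, which expects a larger alcohol effect when hormones are low, also pulls against the SAP sentence.

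**6. Power cost of correction.** Two-sample t test, 30 per group, d = 0.5: power is 0.478 at 0.05 and 0.224 at 0.05/6 = 0.0083. The effect detectable with 80% power rises from d = 0.74 to 0.93. For a correlation (Fisher z) it rises from 0.355 to 0.431 with n = 60, and from 0.492 to 0.585 with n = 30.

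**The case against.** **The counts may not apply.** The SAP places the hormone regressions in SPM12 and writes its outcomes as SPM-style contrasts, which suggests inference on maps. The Data Monitoring Plan mentions SPM and SPSS, but for all data types together, so SPSS may be meant for the non-imaging data. Percent signal change in regions is the only real pointer to extracted values. This stands: every percentage above is conditional. The gap remains on either reading, because maps without a stated threshold or search volume leave the result equally open.

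**The wrong sign does not count in the sex test.** This also stands. A reader might apply 11–25% to all three analyses, but a region where men show the larger alcohol effect would not support the stated hypothesis.

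**Estradiol is already the focus.** True. A reader might infer that three hormones by six regions in two regressions, plus the sex test, give 42 tests and a false-positive rate near 88%. The documents do not support that: Aims 1 and 3 and both SAP hormone hypotheses name estradiol alone. What is missing is a statement that makes it primary and the other two secondary. Pooling the three analyses (18 tests, 60% if independent) is also too strong, because they serve separate stated hypotheses and nothing says that any one success suffices.

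**Imaging work of this kind is exploratory.** The plan declares a primary outcome and directional hypotheses, so this does not excuse the gap. The SAP check that the contrast activates the inhibitory network confirms that the task works. It is not a rule for choosing regions.

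**Averaging the phases would be the tidy remedy.** It would give one value per person, but it discards the within-woman estradiol contrast that the four sessions create and dilutes the Aim 4 prediction about the early follicular phase. It should not be prescribed.

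**Conclusion.** The concern holds within limits. The primary outcome rests on an open list of six regions and feeds three analyses with no inference level, threshold or correction. Estradiol is the only hormone hypothesised but is not designated primary. If extracted values are tested one by one at an assumed two-sided 0.05, the chance of at least one false-positive region is about 11–25% per regression and about 5.5–13% for the directional sex test, over assumed region correlations of 0.9 to 0.3. On SPM maps no figure can be given.

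Separately, the SAP sentence on change in estradiol contradicts Aim 3 and cannot stand beside it. A reader might say the same of the baseline sentence and Aim 1, but one refers to a change and the other to a level, so tension is the right word. What is at stake is how the results can be interpreted. The change should be made before the imaging data are examined.

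**What to change.** In the Statistical Analysis Plan:

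1. Delete *e.g.* and fix the six named regions, with masks and hemisphere set before the data are examined.
2. Make estradiol the primary hormone in both regressions, with progesterone and testosterone secondary.
3. State two-sided 0.05, one inference level and one correction within each analysis. Either use Holm (or an equivalent such as max-T permutation) across the six extracted values, or SPM family-wise correction within one pre-specified mask of those regions. Say that 5% is held per analysis and not across the three. With 0.05/6 per test, the chance of any false positive over all three is about 9–14% at region correlations of 0.7 to 0.3.
4. State how the two cycle phases enter each test, and whether the regressions use 60 participants or the 30 women. If phases are tested separately, extend the correction to those tests.
5. Label other regions and whole-brain maps exploratory.
6. Reconcile the estradiol hypotheses with the Objectives so that one sign counts as the predicted result.

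**Cost.** Text only, with no new data. The price is power for a single region: 48% to 22% at d = 0.5 with 30 per group at the first Holm step. Holm is conservative when regions are correlated, which is the reason to allow max-T permutation. The cost of the mask option cannot be computed, because mask size and smoothness are not given.

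### The SAP's baseline-estradiol analysis is not reconciled with Aim 1: it tests the saline-to-alcohol change rather than the level under alcohol, and its predicted direction runs against the protocol's aims

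*Combined protocol and SAP*

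**What the plan says.** The protocol's Objectives section gives Aim 1 as "To determine the influence of circulating sex hormones on BARI responses to alcohol". The premise for its hypothesis is given first: "Based on the positive relation between estradiol and BARI in sober heavy drinking women". The hypothesis drawn from that premise reads: "we hypothesize that baseline levels of estradiol will be positively related to BARI following alcohol". Under Aim 2 the investigators expect that "women will be more sensitive to the impairing effects of alcohol on BARI in the early follicular phase, when hormone levels are low". Aim 4 keeps that direction, expecting that "the sex difference will be most pronounced for women in the early follicular phase". Aim 3 concerns hormone change, not baseline level, and expects that "less alcohol-induced increase in estradiol will predict greater alcohol-induced decrease in BARI".

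The Statistical Analysis Plan, placed after the study drug attachments, has one analysis of baseline hormones: "regression analyses in SPM12 to assess the degree to which baseline hormone levels predict change in BARI following alcohol compared to saline", on the StopInh>Go, Saline>Alcohol contrast. Its predicted direction is: "We hypothesize that greater baseline E2 will predict less activation following alcohol compared to saline". Its last sentence, on hormone change, predicts that a larger alcohol-induced rise in E2 goes with a larger fall in activation.

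The SAP lists no model of BARI in the alcohol sessions alone and no comparison of early follicular with mid-luteal sessions. It does not say whether the hormone regressions include men. Neither the SAP nor the Data Monitoring Plan gives an alpha level or says whether tests are one- or two-sided.

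**The concern.** The Aim 1 hypothesis and the SAP sentence name different quantities. One is the relation of E2 to activation measured under alcohol. The other is the relation of E2 to the drop from saline to alcohol. A slope on a level and a slope on a difference can have different signs in the same data.

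The directions also differ in spirit. The aims read as though higher estradiol goes with better-preserved activation; the SAP expects higher estradiol to go with a larger loss.

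BARI is the primary outcome in the Study Design section, and hormonal determinants of alcohol's effect on it are the overall objective. If the two sections stay as they are, a reader of the results cannot tell which E2 relation was prespecified for Aim 1, or which sign would count as support.

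**Working it through.** The plan gives no power, alpha or effect-size figure for this analysis, so there is no number to reproduce. The check is of signs.

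**Notation.** Let bS and bA be the slopes of BARI on baseline E2 in the saline and alcohol sessions. Let D = saline BARI - alcohol BARI, which is what the Saline>Alcohol contrast measures; a larger D is a larger drop under alcohol. If E2 is taken as the same in both sessions, the slope of D on E2 is bS - bA.

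**What each statement requires**

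| Source | Statement | In symbols |
|---|---|---|
| Aim 1 rationale | E2 and BARI positively related when sober | bS > 0 |
| Aim 1, read as a level | E2 positively related to BARI under alcohol | bA > 0 |
| Aim 1, read as a response | Higher E2, activation better maintained from saline to alcohol | bA - bS > 0 |
| SAP, baseline E2 | Higher E2, less activation under alcohol than saline | bS - bA > 0 |
| Aims 2 and 4, if carried by E2 | Larger drop when hormones are low | bS - bA < 0 |

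**Level reading.** The SAP condition is bA < bS. Aim 1 is bA > 0. Both hold when 0 < bA < bS. Aim 1 holds and the SAP prediction fails when bA > bS > 0. The SAP prediction holds and Aim 1 fails when bA < 0 < bS. The sign of the change slope therefore neither confirms nor refutes the level hypothesis.

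**Response reading.** Aim 1 needs bA - bS > 0 and the SAP predicts bS - bA > 0. These exclude each other.

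**Illustration.** With equal SDs in the two sessions (assumed, set to 1), cov(E2, D) = rS - rA and var(D) = 2(1 - rho), where rS and rA are the correlations of E2 with BARI under saline and alcohol and rho is the correlation between the two sessions. So

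corr(E2, D) = (rS - rA) / sqrt(2(1 - rho)).

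Take rS = 0.4 (assumed), in line with the Aim 1 rationale. At rho = 0.5 the denominator is sqrt(1) = 1.

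| rA | rho = 0.3 | rho = 0.5 | rho = 0.7 | Direction of the change |
|---|---|---|---|---|
| 0.2 | +0.169 | +0.20 | +0.258 | as the SAP predicts |
| 0.4 | 0 | 0 | 0 | none |
| 0.6 | -0.169 | -0.20 | -0.258 | as Aims 2 and 4 suggest |

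Aim 1 as a level is true in every row. The change correlation takes all three signs, and rho alters its size but never its sign.

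**Hormone change.** Let g be the slope of D on the alcohol-induced change in E2. Aim 3 predicts g < 0 (smaller rise, larger drop). The SAP's last sentence predicts g > 0 (larger rise, larger drop). This reversal depends on no choice of reading.

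**The case against.** The strongest reply is that Aim 1 is tested. Its objective speaks of responses to alcohol, a response is a change, and the SAP regresses that change on baseline hormones. A reader might infer from the hypothesis sentence that Aim 1 is never tested; the documents support that only on the literal level reading. On the other reading the test exists and the fault is its sign. Either way the two sections need reconciling.

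Second, Aim 1 as a level and the SAP prediction are compatible when 0 < bA < bS, which agrees with the sober relation the protocol cites. That stands. It means the SAP analysis is uninformative about the level claim, not that the two contradict each other.

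Third, a reader might infer that the SAP flatly contradicts Aim 2. That goes too far. Aim 2 compares phases within women and refers to hormone levels in general. Progesterone also changes with phase, and a phase effect does not fix the E2 slope. The protocol's own reason, low hormone levels, makes the tension real but inferential.

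Fourth, a reader might infer that Aim 1 cannot be falsified because either sign could be claimed as support. The SAP commits to one sign, and no one-sided test is stated. Under a two-sided test an effect in the other direction would be seen and reported.

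Finally, the SAP sentence may be a slip over the sign of the Saline>Alcohol contrast, with a smaller difference intended. That would remove the direction conflict, but it is not the plain reading, and the SAP's last sentence points the same way as the plain reading. The documents do not say whether this is a slip or a changed hypothesis.

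**Conclusion.** The point holds in a limited form. The SAP's baseline-E2 analysis and the Aim 1 hypothesis are not reconciled: on the level reading the hypothesis has no stated test, and on the response reading it is tested with the reverse prediction. No third reading that keeps the plain sense of both sentences removes the problem. The tension with Aims 2 and 4 is supporting evidence by inference. The reversal of Aim 3 is explicit and shows that the mismatch is not confined to one sentence.

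The conclusion rests on wording and algebra alone. It needs no assumption about effect size, alpha or sidedness; the correlations above are assumed values that only illustrate it. No loss of power is claimed. What is at stake is what Aim 1 can conclude about the primary outcome, so this should be settled before the analysis is run.

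**What to change.** 1. Model BARI in the regions of interest on session baseline E2, infusion (alcohol or saline) and E2 x infusion, with a participant effect for the repeated sessions (four per participant) and a phase term. State whether phase also interacts with infusion, since that changes what the E2 x infusion coefficient means, and whether the model is fitted in women only.
2. Report two results from it: the E2 slope under alcohol, which is Aim 1 as worded, and the E2 x infusion term, which is the change the SAP now targets.
3. Reconcile the Objectives and the SAP to one predicted sign for each term before analysis, or declare the tests two-sided. The choice of sign is the investigators'. Rewrite the SAP's baseline-E2 sentence to match.
4. Reconcile Aim 3 with the SAP's last sentence in the same revision.

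The cost is SAP wording and one extra model. The hormone and imaging data are already part of the study, and no new data are needed.
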